13.2. Sample Size and Randomization

- 13.2.1. Power analysis: This pilot study is designed to determine tolerability and safety of valganciclovir as add-on therapy to pirfenidone. Pirfenidone is reported to be discontinued in 13% of subjects due to adverse events, almost all of which occur within the first 4 weeks of treatment (based on AE profiles from the ASCEND study). Therefore, we do not expect any

placebo treated subjects to withdraw from this study. Using a 2:1 randomization (valganciclovir:placebo) and enrolling 30 subjects will allow us to detect an increased withdrawal rate in the valganciclovir group in the range of 25% (75% power with a one-sided $\alpha=0.1$). Subjects who require dose reduction, or temporary discontinuation but are able to resume treatment will be considered non-withdrawals.

13.2.2. **Randomization:** The randomization scheme will be a ratio of 2:1 for drug versus placebo. Once a participant has signed the consent form and completed the enrollment visit (and baseline bronchoscopy in subjects who participate in the bronchoscopy substudy), the participant will be randomized. Study medication will be distributed by the VUMC investigational pharmacy according to the randomization scheme.

13.3. **Statistical analysis:** For the primary endpoint, the rate-of-discontinuation of study drug due to adverse events will be compared between valganciclovir and placebo subjects by Chi-square. **Secondary analysis:** Frequencies of specific adverse event profiles will be compared between groups by Chi-square. This study is not powered to detect clinically significant changes in pulmonary function or perform multivariate analyses. Exploratory analyses for physiologic and biochemical endpoints will be performed using standard nonparametric statistics or paired tests when appropriate. The rate of change in FVC (cc/year) will be compared between valganciclovir therapy group (treatment group) compared to the standard of care (placebo) group. For other physiologic measurements (6MWD, oxygenation), similar analyses will be performed. For exploratory biomarker studies, paired analyses (Baseline vs. 12 weeks) will be performed comparing subjects randomized to valganciclovir or placebo. All analyses will be performed using STATA 11.0 (StataCorp, College Station, TX) and the programming language R (50).

14. Safety and Adverse Events Monitoring: Study personnel will meet bi-weekly to review all safety laboratory data collected on each subject and review all adverse events. The study investigators will decide the appropriate steps to be taken to include dose modifications, and further monitoring. [name] will act as an on-site medical monitor who can become un-blinded to study drug if needed in order to adjudicate side effects are detected and whether they may due to valganciclovir. Planned safety analyses will occur after enrollment of 10 and 20 subjects by the medical monitor. If 5 more subjects have withdrawn from the study due to adverse events in the valganciclovir arm compared to placebo at either interim analysis, the study will be terminated.

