- 7.1.4. tolerance of full-dose (2403 mg/day) pirfenidone
- 7.1.5. Positive serology for EBV or CMV

7.2. **Exclusion criteria** will be:

- 7.2.1. FVC $\leq 40\%$ predicted
- 7.2.2. DLCO $\leq 35\%$ predicted (Crapo)
- 7.2.3. FEV1/FVC < 0.7
- 7.2.4. Significant centrilobular emphysema ($> 40\%$ by HRCT)

- 7.2.5. Active tobacco use (cigarette or cigar smoking)
- 7.2.6. Resting SpO₂ on room air <89%
- 7.2.7. listed for lung transplantation defined as being assigned a lung allocation score
- 7.2.8. environmental exposure (occupational, environmental, drug, etc.) felt by the principal investigator (PI) to be the etiology of the interstitial disease
- 7.2.9. diagnosis of collagen-vascular conditions (according to the published American College of Rheumatology criteria)
- 7.2.10. history of unstable or deteriorating cardiac disease
- 7.2.11. acute coronary syndrome, coronary artery bypass, or angioplasty within 3 months of screening
- 7.2.12. uncontrolled arrhythmia
- 7.2.13. uncontrolled hypertension
- 7.2.14. known HIV or hepatitis C
- 7.2.15. known cirrhosis or chronic active hepatitis
- 7.2.16. active substance or alcohol abuse
- 7.2.17. pregnancy or lactation
- 7.2.18. Women of childbearing potential who are not using a medically approved means of contraception. Subjects will be considered of childbearing potential if they are not surgically sterile or have not been postmenopausal for at least 2 years [any subject who is postmenopausal for < 2 years will be required to have a follicle-stimulating hormone (FSH) level to assess her potential to become pregnant
- 7.2.19. clinically relevant lab abnormalities (obtained within 30 days before enrollment), including:
 - 7.2.19.1. creatinine > 2 x upper limit of normal (ULN)
 - 7.2.19.2. hematology outside of specified limits: white blood cells (WBCs) < 3,500/mm³; hematocrit < 25% or > 59%; platelets < 100,000/mm³
 - 7.2.19.3. total bilirubin > 2 x ULN
 - 7.2.19.4. Aspartate (AST) or alanine aminotransferases (ALT) (serum glutamic-oxaloacetic; transaminase [SGOT], or serum glutamic pyruvic transaminase [SGPT]) > 2.0 x ULN
 - 7.2.19.5. alkaline phosphatase > 3 x ULN
 - 7.2.19.6. albumin < 3.0 mg/dL at screening
- 7.2.20. known hypersensitivity to study medication
- 7.2.21. any condition that, in the judgment of the PI, might cause participation in this study to be detrimental to the subject or that the PI deems makes the subject a poor candidate

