- 10.1. Screening visit: Once informed consent is obtained, subjects may begin the screening process. If a study subject has been evaluated at VUMC by a study physician and has performed clinical testing that meets study guidelines within 30 days, then this testing maybe used to qualify for study entry. This will facilitate entry into the study, avoid repeated testing, and reduce costs. The following procedures will be performed at screening: 1) medical history and physical examination; 2) vital signs including oximetry; 3) blood chemistries, hematology counts; EBV and CMV serology 4) PFTs including spirometry, lung volumes, and diffusing capacity; 5) HRCT review; 6) surgical lung biopsy review; and 7) recording of current medications. If patients are not taking pirfenidone at the time of screening, then patients will be placed on pirfenidone and will be re-assessed to determine study eligibility 4 weeks later to allow ample time to determine tolerance to pirfenidone.
- 10.2. Enrollment visit: For subjects who meet eligibility criteria, enrollment may occur the same day as the screening visit. For subjects who require blood tests to be drawn at the screening visit, they will be notified by telephone of their eligibility for the study and study drug will be mailed to subjects by the investigational drug pharmacy. Randomization will be 2:1 valganciclovir versus placebo. Subjects will be offered the opportunity to undergo an optional research bronchoscopy. For subjects who undergo bronchoscopy, study drug will begin immediately following the bronchoscopy. Subjects who do not undergo bronchoscopy will begin study drug immediately. Additional tests that will be obtained are the following: 1) six minute walk test (6 MWT); 2) baseline blood chemistries and blood counts if >30 days after the screening visit; 3) baseline blood draws for biomarker and immunology studies, including HLA-typing; 4) teaching subjects self-monitoring and diary recording; and 5) optional bronchoscopy with BAL. Bronchoscopy will be the last test performed at enrollment.

- 10.3. Week 4 and 8 study visits: The primary purpose of these visits is to establish safety of study treatment and adherence to study treatment. Subject's diaries will be reviewed, medical history and physical examination will be performed, a pill count will be performed, current medications will be recorded, and chemistries and hematology counts will be obtained.

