14.1 ASSESSMENT OF SAFETY

Specification of Safety Variables

Safety assessments will consist of monitoring and reporting adverse events (AEs) and serious adverse events (SAEs) that are considered related to {study drug}, all events of death, and any study specific issue of concern.

Adverse Events

An AE is any unfavorable and unintended sign, symptom, or disease temporally associated with the use of an investigational medicinal product (IMP) or other protocol-imposed intervention, regardless of attribution.

This includes the following:

- AEs not previously observed in the subject that emerge during the protocol-specified AE reporting period, including signs or symptoms associated with idiopathic pulmonary fibrosis that were not present prior to the AE reporting period.
- Complications that occur as a result of protocol-mandated interventions (e.g., invasive procedures such as cardiac catheterizations).

If applicable, AEs that occur prior to assignment of study treatment associated with medication washout, no treatment run-in, or other protocol-mandated intervention.

Preexisting medical conditions (other than the condition being studied) judged by the investigator to have worsened in severity or frequency or changed in character during the protocol-specified AE reporting period.

Serious Adverse Events

An AE should be classified as an SAE if the following criteria are met:

- It results in death (i.e., the AE actually causes or leads to death).
- It is life threatening (i.e., the AE, in the view of the investigator, places the subject at immediate risk of death. It does not include an AE that, had it occurred in a more severe form, might have caused death.).
- It requires or prolongs inpatient hospitalization.
- It results in persistent or significant disability/incapacity (i.e., the AE results in substantial disruption of the subject's ability to conduct normal life functions).
- It results in a congenital anomaly/birth defect in a neonate/infant born to a mother exposed to the IMP.
- It is considered a significant medical event by the investigator based on medical judgment (e.g., may jeopardize the subject or may require medical/surgical intervention to prevent one of the outcomes listed above).

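### The 75% power in section 13.2.1 rests on a zero placebo withdrawal rate that the eligibility and enrollment rules do not secure for existing pirfenidone users

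*Combined protocol and SAP*

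**What the plan says.** Section 13.2.1 builds the power statement in three steps.

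- Background rate: "Pirfenidone is reported to be discontinued in 13% of subjects due to adverse events, almost all of which occur within the first 4 weeks".
- Inference: the plan therefore expects no "placebo treated subjects to withdraw from this study".
- Power: "Using a 2:1 randomization (valganciclovir:placebo) and enrolling 30 subjects" is said to allow the study to "detect an increased withdrawal rate in the valganciclovir group in the range of 25" percent, with 75% power at a one-sided alpha of 0.1. No formula or test is named there. Section 13.3 names a chi-square test without giving its sidedness.

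Three rules decide who can be randomized in relation to that 4-week window.

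- Section 7.1.4 requires "tolerance of full-dose (2403 mg/day) pirfenidone", with no minimum time on the drug.
- Section 10.1: "If patients are not taking pirfenidone at the time of screening, then patients will be placed on pirfenidone and will be re-assessed" for eligibility 4 weeks later. This covers non-users only.
- Section 10.2 lets an eligible subject enroll on the day of screening.

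No exclusion criterion in section 7.2 sets a minimum time on pirfenidone. Section 9 puts the clinic's current pirfenidone users at about 125 but does not say how long they have been treated.

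**The concern.** The step from discontinuations concentrated in the first 4 weeks to no placebo withdrawals is valid only if subjects are past those weeks when randomized. The protocol arranges this for patients whom the study itself starts on pirfenidone. It does not arrange it for patients who started in routine care shortly before screening. An existing user who has reached and tolerates full dose could be enrolled while still inside the window that 13.2.1 treats as the risk period.

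The primary comparison in section 13.3 has only 10 placebo subjects, so a single placebo withdrawal changes it sharply. The plan gives power at one placebo rate, the most favourable one, and shows no sensitivity to it.

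**Working it through.** **Inputs from the documents.** 20 valganciclovir and 10 placebo subjects (6.1); one-sided alpha 0.10, target increase about 25 points, placebo rate 0% (13.2.1); chi-square (13.3); 13% pirfenidone discontinuation (13.2.1).

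**Inputs assumed.** The documents give no non-zero placebo rate. I use 5%, and also 1.3%, which is 10% of subjects being recent starters who each carry the full 13% risk (0.10 × 0.13 = 0.013). For each placebo rate pC, the valganciclovir rate pT is either pC + 25 points or held at 25%.

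**Step 1: reproduce the plan's figure.** Pooled normal approximation, no continuity correction:

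power = Φ{[(pT − pC) − 1.2816 × SE0] / SE1}, where SE0 = √[p̄(1 − p̄)(1/20 + 1/10)], SE1 = √[pT(1 − pT)/20 + pC(1 − pC)/10] and p̄ = (20pT + 10pC)/30.

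At 25% versus 0%: p̄ = 0.1667, SE0 = 0.1443, SE1 = 0.0968. Then (0.25 − 0.1850)/0.0968 = 0.672 and Φ(0.672) = 74.9%. This matches the stated 75%, though the plan does not say that this formula was used.

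**Step 2: non-zero placebo rate, same approximation.**

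- 30% versus 5%: SE0 = 0.1596, SE1 = 0.1235; (0.25 − 0.2045)/0.1235 = 0.369; power 64.4%.
- 25% versus 5%: SE0 = 0.1499, SE1 = 0.1188; (0.20 − 0.1921)/0.1188 = 0.067; power 52.7%.
- 26.3% versus 1.3%: power 71.5%, a loss of about 3 points.
- 25% versus 1.3%: power 68.6%, a loss of about 6 points.

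**Step 3: exact check.** Enumerate all binomial outcomes and reject when the uncorrected one-sided chi-square has p < 0.10.

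| Valganciclovir v placebo | Normal approximation | Exact chi-square |
|---|---|---|
| 25% v 0% | 74.9% | 90.9% |
| 26.3% v 1.3% | 71.5% | 84.4% |
| 25% v 1.3% | 68.6% | 82.2% |
| 30% v 5% | 64.4% | 71.0% |
| 25% v 5% | 52.7% | 61.5% |

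The exact test drops below 75% only at a placebo rate of about 2.5% (valganciclovir held at 25%) to about 4% (25-point increase kept).

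**Step 4: why one placebo event matters.** With 0 of 10 placebo withdrawals, 3 of 20 on valganciclovir reach p < 0.10. With 1 of 10, it takes 7 of 20. At a true valganciclovir rate of 25%, the chance of reaching the threshold falls from 90.9% to 21.4%. At a 5% placebo rate, the chance of at least one event among 10 is 1 − 0.95^10 = 40%. At 1.3% it is 1 − 0.987^10 = 12%.

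**The case against.** The strongest reply is that the stated power is correct for the stated inputs, and that nothing shows zero to be unrealistic. The expected pool is about 125 patients already treated, and recent starters may be rare. Requiring tolerance of full dose removes some early intolerance before randomization. The 13% is discontinuation of pirfenidone, while the endpoint is discontinuation of study drug, so it is only a rough proxy. The choice of test also moves power more than this issue does: at 25% versus 0%, exact power is 90.9% for the uncorrected chi-square and 38.3% for Fisher's test. All of this stands, and it limits the point to a premise that is not secured.

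Three stronger readings are tempting, and the documents do not support them.

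- A reader might infer that power is overstated outright. That depends on how many subjects are randomized early in pirfenidone treatment, which the documents do not give.
- A reader might infer that stopping pirfenidone counts as a primary event. Nothing says so. Section 13.2.1 treats dose reduction, or interruption with resumption, as non-withdrawal.
- A reader might point to the adverse event definition in section 14.1, "including signs or symptoms associated with idiopathic pulmonary fibrosis that were not present prior to the AE reporting period", as a source of placebo withdrawals. That passage governs what is recorded as an adverse event. It does not say when study drug is stopped.

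What the reply does not remove is the mismatch between the 4-week argument in 13.2.1 and a 4-week interval that applies only to non-users.

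**Conclusion.** The point holds as a gap between the power premise and the enrollment rules. At an assumed 5% placebo rate, power falls below 75% by either method: to 64.4% or 52.7% by the approximation, and to 71.0% or 61.5% by the exact uncorrected chi-square. At an assumed 1.3% the effect is small, about 3 to 6 points by the approximation, and the exact test stays above 75%. Both rates are assumptions, and which is nearer the truth cannot be settled from the documents. The issue is worth correcting because the primary comparison is sensitive to a single placebo withdrawal and the plan shows only the zero case.

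**What to change.** Reconcile sections 7.1.4, 10.1 and 10.2 with 13.2.1, so that the 4-week premise of the power statement holds for every randomized subject, including those already taking pirfenidone at screening.

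In 13.2.1, restate power over a range of non-zero placebo rates, for example 1% to 5% and labelled as assumptions, beside the 0% case. Name the test and its sidedness, and say whether the valganciclovir rate is held at 25% or moves with the placebo rate. This is needed in any case: a 4-week minimum would not guarantee zero, because the plan itself says almost all rather than all, and placebo subjects can stop for other adverse events.

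The cost is a short delay for a few recent starters and a less favourable stated power. No extra patients are needed.

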3.1 To determine the safety and tolerability of oral valganciclovir as add-on therapy in patients with IPF tolerating standard treatment with pirfenidone. 30 individuals with a diagnosis of IPF and positive serology for EBV or CMV will be enrolled in this study at Vanderbilt University Medical Center and randomized to receive either valganciclovir or placebo in a 2:1 ratio for 12 weeks. The primary endpoint will be rate of discontinuation of study drug due to adverse events in subjects randomized to valganciclovir compared to placebo. In addition, we will compare type, frequency and duration of adverse events (AE) and serious adverse events (SAE) between valganciclovir and placebo subjects.

3.2 To investigate the effect of anti-herpesvirus treatment on changes in viral load and immune responses against herpesvirus. A subset of study subjects will undergo bronchoscopy with BAL at the time of study entry and at 12 weeks for measurement of: 1) immune response to herpesviruses in lung lymphocytes and 2) herpesvirus DNA in cell-free BAL fluid. Additional studies to investigate changes in the immune response in peripheral blood lymphocytes to herpesviruses will include: 1) analyzing PD-1 expression by T lymphocytes and 2) quantifying CD8+ T cell immune responses to herpesvirus antigens at study entry and after 12 weeks of therapy. These parameters will be reassessed at 6 months and 1 year after study entry

to determine whether changes in anti-herpesvirus immune responses persist or revert to pre-treatment levels, thus shedding light on the duration of therapy needed to potentially alter disease progression.

4. Endpoints

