4.1. Primary Endpoint

4.1.1. The primary outcome will be safety and tolerability will be determined by type, frequency and duration of adverse events (AE) and serious adverse events (SAE) in subjects receiving valganciclovir versus placebo.

4.2. **Secondary Endpoints:** We will evaluate for trends in other clinical endpoints, as well as viral and immune endpoints over time in the valganciclovir group compared to the placebo group.

4.2.1. We will determine the change in pulmonary function tests including forced vital capacity (FVC) and diffusing capacity for carbon monoxide (DLCO) in the valganciclovir treated group compared to placebo during active treatment and post-treatment follow-up. PFTs will be measured at baseline, 3 months (12 weeks), 6, 9 and 12 months after randomization to determine the FVC slope (change in FVC over time) and change in diffusion capacity (DLCO).

4.2.2. We will determine the effect of valganciclovir therapy on viral load in cell-free BAL fluid.

4.2.2.1. We will evaluate the change from baseline in daytime oxygen requirements. Oxygen requirements will be measured at study visits baseline, 3, 6, 9, 12 months. At each study visit, while at rest, the subject will be placed on the amount of supplemental O₂ required at the enrollment visit. After 5 minutes, the SpO₂ on this supplemental flow rate will then be recorded and evaluated in comparison to baseline. In addition, the patient will have his/her supplemental oxygen requirement determined to maintain oxygen saturation $\geq 88\%$ at rest. The change in liters per minute flow rate in oxygen compared to baseline will be recorded.

4.2.3. Exercise capacity will be determined on the basis of the 6 minute walk test (6MWT). The principal exercise capacity measurement will be the change in distance until SpO₂ reaches 80% compared to baseline. 6 MWT will be measured at study visits baseline, 3, 6, 9, 12 months. The 6MWT will be performed using a standardized protocol while the subject is breathing room air (i.e. without supplemental oxygen).

4.2.4. Additional secondary endpoints will analyze the immune response to herpesviruses by analyzing PD-1 expression by T lymphocytes and quantifying CMV- and EBV-antigen specific CD8⁺ T cell immune responses.

5. Background and Significance

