- 10.4. Week 12 study visits: This visit will conclude active treatment in the study and will be the primary endpoint for safety and tolerability. In addition, 6 MWT, and oximetry will be performed at this study visit. Subject's diaries will be reviewed, medical history and physical examination will be performed, PFTs will be obtained according to usual clinical care protocol, a pill count will be performed, current medications will be recorded, chemistries/hematology counts will be obtained, and blood will be obtained for biomarker and immunology studies. Subjects who consent to research bronchoscopy will undergo a second research bronchoscopy coordinated with the week 12 study visit.
- 10.5. Week 16 telephone call: 4 weeks after the final study visit (week 12), subjects will be contacted by telephone to review any side effects that occurred while taking study drug.
- 10.6. 6, 9, and 12 month visits: These visits will coincide with routine clinical care visits. Medical history and physical examination will be performed, and PFTs, 6MWT and oximetry will be performed according to usual clinical care protocol studies. A blood sample will be obtained for immunology studies.
- 10.7. Unscheduled disease progression visits: If a subject is found to have new symptoms or worsening of dyspnea or oxygen utilization, the subject will be scheduled for a clinic visit as soon as feasible to reassess secondary endpoints.
- 10.8. Table of Study Visits:

	Screening/ Enrollment Visit	Bronchoscopy Visit (optional)	Week 4 (study visit)	Week 8 (study visit)	Week 12 (study visit)	Week 16 (Teleph one call)	Month 6 (with clinical visit)	Month 9 (with clinical visit)	Month 12 (with clinical visit)
Consent	X								
Randomization	X								
Medical History	X				X				
Physical Exam	X				X				
Blood Chemistry (CMP; CBC, pregnancy test if applicable)	X		X	X	X				
Dispense study drug	X	(X)							
T cell studies from peripheral blood	X	(X)			X		X	X	X
Spirometry Test/DLCO	X				X		X	X	X
6 MWT	X				X		X	X	X

Bronchoscopy (if patient consents)		X			X				
Dispense Study/Review Study Diary for compliance evaluation	X		X	X	X				
Adverse Events			X	X	X	X	X	X	X

11. Data Collection for Specific Aims

11.1. Aim 1: To determine the safety and tolerability of oral valganciclovir as add-on therapy in patients with IPF tolerating standard treatment with pirfenidone.

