11.1.1. Rationale: This study is designed to assess for safety and tolerability of valganciclovir in IPF patients who are taking standard therapy for IPF (pirfenidone) as assessed by type, frequency and duration of AE and SAEs. Exploratory secondary analysis to evaluate for clinical efficacy will include changes in FVC slope of patients with IPF, oxygenation, and exercise capacity. In addition to identifying whether anti-viral therapy could positively impact any of these parameters, collecting these data will ensure that any detrimental effects of the drugs used to treat herpesviruses on clinically relevant endpoints will be identified. Information will be collected as outlined below. For analysis of all these variables, the standard treatment arm with pirfenidone and placebo will be compared to valganciclovir and pirfenidone.

11.1.2. Evaluation for safety of valganciclovir. Assessment of safety will be determined by ongoing review of clinical laboratory tests (blood sampling for clinical laboratory parameters-see schedule of events), physical examination including vital sign measurements, functional status assessments and adverse events. Women of childbearing potential will undergo a urine pregnancy test at each study visit.

11.1.3. Evaluation for treatment emergent adverse events. A treatment-emergent adverse event (TEAE) is defined as a sign or symptom that emerges during treatment or within the 12 weeks following the last dose of the study drug, having been absent pretreatment or that has worsened relative to the pre-treatment state. Any adverse event deemed related to study drug will also be considered a TEAE regardless of elapsed time since last study drug dose. Adverse events will be graded using National Cancer Institute [NCI] CTCAE Version 3.0 during the study evaluation. Study drug-related adverse events will be listed individually.

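### No blood count or chemistry is scheduled after week 12 to date or detect late lab toxicity, and no planned analysis shows whether the 900 mg/day dose was kept

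*Combined protocol and SAP*

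**What the plan says.** **Outcome.** Section 4.1.1 defines the primary outcome through "type, frequency and duration of adverse events (AE) and serious adverse events (SAE) in subjects receiving valganciclovir versus placebo". Section 3.1 makes the discontinuation rate the primary endpoint and adds that "we will compare type, frequency and duration of adverse events (AE) and serious adverse events (SAE) between valganciclovir and placebo subjects". Section 14.2 requires every AE to carry start and end dates and a record of the action taken.

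**Lab schedule.** Section 11.1.2 rests lab safety on "blood sampling for clinical laboratory parameters-see schedule of events". In the visit table (10.8), the row that begins "Blood Chemistry (CMP; CBC, pregnancy test if applicable" is marked at screening/enrollment and weeks 4, 8 and 12, and is blank afterwards. At week 16, "subjects will be contacted by telephone to review any side effects that occurred while taking study drug" (10.5). For months 6, 9 and 12, section 10.6 says "A blood sample will be obtained for immunology studies" and names no safety labs. The adverse-event row is marked at all of these later contacts.

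**Windows.** A TEAE is one that "emerges during treatment or within the 12 weeks following the last dose of the study drug" (11.1.3). Routine AE reporting under 14.2 closes earlier, 30 days after the last dose.

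**Dose rule and test.** Section 8.1 justifies 900 mg once daily. Under 8.3 a lab abnormality possibly related to drug leads first to a hold and resumption, then on recurrence to 450 mg once daily, and to termination only if there is trouble again at 450 mg. Section 13.2.1 adds: "Subjects who require dose reduction, or temporary discontinuation but are able to resume treatment will be considered non-withdrawals". The primary chi-square in 13.3 compares discontinuations due to AEs. A second chi-square compares frequencies of specific AEs. Nothing in 13.3 covers holds, reductions or duration. The section 14 stopping rule also counts withdrawals only.

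**The concern.** Marrow suppression is found by blood test, so a telephone call or a history cannot show that counts have recovered. If the last scheduled count is on the last treatment day, the end dates that 14.2 asks for depend on tests nobody is told to order, and no later analysis can supply them. The post-treatment part of both windows also depends on symptoms or on an investigator's decision to test.

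The dose question is separate. A subject can fail the justified dose twice, finish on half of it, and be scored the same as someone who took 900 mg/day throughout. A report of no excess in discontinuations could then be read as support for 900 mg/day in a next trial, although the planned analyses would not show how many subjects stayed on that dose or whether counts recovered.

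**Working it through.** **1. Schedule against windows** (10.5, 10.6, 10.8, 11.1.3, 14.2; last dose at week 12)

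| Time | CBC/chemistry scheduled? | What happens |
|---|---|---|
| Screening, weeks 4 and 8 | Yes | |
| Week 12 | Yes | Treatment ends |
| Week 16 (28 days after last dose) | No | Telephone call |
| About week 16.3 (12 + 30/7) | – | Routine AE reporting closes |
| Week 24 (12 + 12) | – | TEAE window closes |
| Month 6 (about week 26) | No | Blood for immunology |

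Neither window contains a scheduled post-treatment lab test. Events found at week 4 or 8 that resolve by week 12 can be dated from later draws and the 8.3 rechecks. The gap covers events first found at week 12, events still present then, and events that arise afterwards.

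To size the first group, assume lab toxicity in a share T of the arm, with equal hazard h in each 4-week interval: h = 1 − (1 − T)^(1/3), and the share first found at week 12 is h(1 − h)²/T. For T = 0.30, h = 0.112 and the share is 0.295. It is 0.309 for T = 0.20 and 0.278 for T = 0.40. With 6 of 20 affected, about 1.8 subjects (6 × 0.295) have no scheduled test to date the end of their event, before adding those still unresolved. If detection rises 1:2:3 across the three visits, the share is 3/6 = 50%.

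**2. The plan's power figure.** Inputs from 13.2.1 and 6.1: 20 v 10, 25% v 0%, one-sided 0.10. The pooled rate is 5/30 = 0.1667. Null SE = √(0.1667 × 0.8333 × (1/20 + 1/10)) = 0.1443. Alternative SE = √(0.25 × 0.75/20) = 0.0968. Power = Φ((0.25 − 1.2816 × 0.1443)/0.0968) = Φ(0.67) = 0.749, so the stated 75% reproduces. It treats all 25% as permanent stops.

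**3. What 8.3 does to that 25%.** Assume 25% have lab toxicity early enough to go through every step, each recurrence has probability q, everyone held can resume, nobody stops for another reason, and no placebo subject stops. The stop rate is 0.25 × q². The uncorrected chi-square first flags at 3/20 v 0/10 (z = 0.15/√(0.1 × 0.9 × 0.15) = 1.29; 2/20 v 0/10 gives 1.04). The exact chance of a flag is therefore P(X ≥ 3) for X ~ Binomial(20, stop rate).

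| q | Stop rate | Chance primary test flags |
|---|---|---|
| All affected stop | 25% | 0.91 |
| 0.9 | 20.25% | 0.80 |
| 0.7 | 12.25% | 0.45 |
| 0.5 | 6.25% | 0.13 |
| 0.3 | 2.25% | 0.01 |

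On the plan's own approximation, 25% stops give 0.75 and 6.25% give 0.25. Subjects held who cannot resume, or stopped early by an investigator, would raise these figures.

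**4. One trial, with assumed counts.** Six of 20 are held, 3 of them are cut to 450 mg, and 1 stops. The primary test on 1/20 v 0/10 gives z = 0.05/√(0.0333 × 0.9667 × 0.15) = 0.72, p = 0.24. Any AE-driven dose change, 6/20 v 0/10, gives z = 0.30/√(0.2 × 0.8 × 0.15) = 1.94, p = 0.026. If one placebo subject is also held, p = 0.11.

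**5. The AE-frequency comparison already planned.** Take 30% lab toxicity, lab AEs grouped, and one-sided 0.10 (13.3 specifies neither grouping nor level). This test flags 96%, 77% and 66% of trials at placebo rates of 0, 5% and 10%. A count of dose changes, with onset spread over the three intervals, flags 83%, 62% and 49% at the same background rates. It is lower because toxicity first found at week 12 can no longer cause a hold, so only 0.30 × (0.374 + 0.332) = 21.2% of the arm contributes.

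**The case against.** The strongest reply is that the plan already looks for this toxicity. AEs are graded by CTCAE, safety labs are reviewed every two weeks, and 13.3 compares AE frequencies; step 5 shows that comparison flags at least as many trials as a dose-change count would. This stands. A reader might infer that the plan hides lab toxicity or cannot show tolerability at all, and the documents do not support that.

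Second, discontinuation under an adjustable regimen is a coherent endpoint, declared in advance. Sections 2 and 3.1 speak of valganciclovir as add-on therapy without naming a dose, and 8.3 makes reduction part of the regimen. This also stands, and it is why the primary test should stay. It does not give 13.3 any analysis of whether the dose justified in 8.1 was kept.

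Third, a reader might infer that 8.3 makes permanent stops rare. The documents give no toxicity, recurrence or non-resumption rate, 8.1 describes 900 mg/day as generally well tolerated, and step 3 runs from 0.01 to 0.80 across plausible recurrence. How often the primary test misses loss of dose is unknown.

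Fourth, unscheduled labs are possible under section 14, and the rechecks in 8.3 date many on-treatment events. The 8.3 rechecks are tied to holding, resuming or reducing drug, and the section 14 provision is discretionary. Neither guarantees a count after week 12.

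**Conclusion.** The point holds as a minor one, in two parts. The first rests on the text alone: no CBC or chemistry is scheduled after week 12, so lab events found or ongoing then have no planned end-date test, and events arising in the 30-day or 12-week window have no planned detection. About 28% to 31% of affected subjects would be first found at week 12 under equal hazard, which is an assumption.

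The second is that the primary test measures tolerance of an adjustable regimen and can miss loss of the 900 mg/day dose, while 13.3 plans nothing that would show it. That it can happen follows from 8.3 with 13.2.1. How often depends on rates the documents do not give. Not all AE durations are lost: lab events that resolve by week 12 can be dated.

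**What to change.** 1. In 10.5 and 10.8, add a CBC and chemistry for every subject at week 16, drawn locally around the telephone call, and repeat it until resolved if abnormal. Week 16 is 28 days after the last dose, inside both windows. The month 6 draw should not be the substitute: at about week 26 it falls 14 weeks after the last dose, outside both. Even if month 6 is taken as week 24, it sits on the last day of the TEAE window and far outside the 30 days.
2. In 13.3, beside the unchanged primary test, report by arm the number of subjects with an AE-driven hold, a reduction below starting dose, or a permanent stop, separately and combined, with the difference and a confidence interval. Using the starting dose as reference keeps renal dosing at entry and the split 450 mg twice-daily schedule from counting as reductions. Label it descriptive or exploratory.
3. State that 900 mg/day will be called tolerated only when this summary and the discontinuation result have been read together.

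The cost is one extra draw for about 30 subjects, one mark in the visit table and a short table in the report. Section 14.2 already records the action taken for each AE. Sample size does not change.
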